In the initial portion (Phase I) we will treat 6 patients with vosaroxin administered intravenously on days 1 and 4 at a dose of 90 mg/m^2 in the first cycle (induction 1) for a total dose of $180 \text{ mg/m}^2/\text{cycle}$ in combination with decitabine at a dose of 20 mg/m^2 intravenously for 5 consecutive days (Days 1 to 5). These doses have been given safely in previous studies as follows. A vosaroxin dose of 90 mg/m^2 was identified as the MTD in the dose-escalation (phase Ib) of the SP0-0012 study. In the phase II of this study 69 patients who had either first relapsed AML (relapse following an initial CR ≥ 3 months and ≤ 24 months) or primary refractory AML (failed to achieve a CR or CRp [CR with incomplete platelet recovery] following 1 or more cycles of induction, or an initial CR < 3 months) were treated with 80 or 90 mg/m^2 vosaroxin on days 1 and 4 in combination with cytarabine either as a continuous intravenous (CIV) infusion ($400 \text{ mg/m}^2/\text{day}$) on days 1-5 or a 2-hour intravenous (IV) infusion ($1 \text{ g/m}^2/\text{day}$) on days 1-5. The combination of vosaroxin at a dose of 90 mg/m^2 and IV cytarabine was well tolerated. Data from the SP0-0012 study provide the preliminary safety and clinical activity information for combination treatment, and formed the basis for the pivotal phase III VALOR study of vosaroxin in combination with cytarabine which is currently ongoing. Decitabine has been approved for treatment of MDS and AML at a dose of $20 \text{ mg/m}^2/\text{day}$ for days 1-5. Decitabine is less cytotoxic, less myelosuppressive and has lower incidence of mucositis than IV cytarabine which has safely been administered in combination with vosaroxin in the SP0-0012 and VALOR studies. Therefore, we anticipate that a starting dose of vosaroxin administered intravenously on days 1 and 4 at a dose of 90 mg/m^2 in the first cycle (induction 1) for a total dose of $180 \text{ mg/m}^2/\text{cycle}$ in combination with decitabine at a dose of 20 mg/m^2 intravenously for 5 consecutive days (Days 1 to 5) would be a reasonable option. These doses have been given safely in previous studies. The purpose of the lead-in phase I portion is to ensure safety. If clinically significant, study drug related grade 3-4 toxicity is observed during the first cycle in 1 or less of 6 evaluable patients treated, the study will transit to the Phase II portion. If clinically significant, study drug related grade 3-4 toxicity is observed during the first cycle in 2 or more of 6 evaluable patients treated, six additional patients will be treated on the Phase I portion at a lower dose level (see section 4.4 and section 10.2) until we define a Phase II safe dose schedule at which 1 or less out of 6 evaluable patients on the Phase I experience clinically significant, study drug related grade 3-4 toxicity during the first cycle. After the Phase I portion ensures safety thereby defining the Phase II dose schedule, all subsequent patients will receive the same dose schedule in the Phase II portion. This Phase II portion will include up to a total of 60 evaluable patients.

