will be submitted to investigational new drug (IND) office for review. Cohort summaries will also be submitted when going to a lower dose cohort in phase I. Once approved, the Phase II portion of the study will be opened. Up to 60 patients will be treated on the Phase II portion. The primary endpoint of the Phase II study will be efficacy as measured by ORR rate. Early stopping rules will be implemented for excessive toxicity or lack of efficacy. Please refer to statistical section 10.2 for details.

4.2 General Study Treatment Plan:

All chemotherapy infusions will be done at MDACC only. The intent of the study design is for all patients to receive up to 7 courses, including up to two courses of induction therapy and up to five courses of consolidation therapy. Treatment will be continued during the duration of the study unless patients exhibit evidence of treatment failure, disease progression, experience an unacceptable toxicity, or the investigator determines that discontinuation of treatment is in the best interest of the patient. Patients will be treated with study drugs based on a calculation determined from the patient's body surface area (BSA). BSA will be calculated before each cycle and will be based on the patient's height (measured at baseline) and weight (measured each cycle). Dosing of both drugs will be based on actual body weight with no capping of dose based on BSA.

4.3 Induction Therapy in Phase 1:

The first 6 patients on study (first cohort) will receive 1 or 2 induction cycles of therapy according to the following starting schedule: vosaroxin will be administered intravenously as a short infusion over 8 to 10 minutes on days 1 and 4 at a dose of 90 mg/m^2 in the first cycle (induction 1) for a total dose of $180 \text{ mg/m}^2/\text{cycle}$ in combination with decitabine at a dose of 20 mg/m^2 administered as a continuous intravenous infusion over approximately 1 hour given daily for 5 consecutive days (Days 1 to 5). These doses have been given safely in previous studies. If a dose is missed, the patient may take the missed dose if it has been less than 48 hours.

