Patients, who have not achieved remission (CR, CRp, Cri) following the initial induction (induction 1) course, can receive one additional induction course (induction 2) at the same dose as induction 1 to optimize response if indicated. The re-induction must be given within 4-8 weeks of documented refractory leukemia. Re-induction (Induction 2) may be given beyond the stipulated 8 weeks if approved by the study PI.

If the bone marrow aspirate and/or biopsy(s) performed after the induction courses reveal a remission marrow (CR/CRp/CRi), then the patient may proceed to consolidation therapy at the discretion of the treating investigator. In addition, any clinically significant drug-related, nonhematologic toxicity experienced by a patient should return to < grade 2 or the baseline grade before the patient continues treatment.

Should the patient not achieve CR/CRp/CRi after the second induction course, they will be taken off study unless clinical benefit is observed and the PI approves continuation of therapy on the protocol.

Hydroxyurea 1.5 g orally daily for up to 10 days is allowed in the first induction course for white blood count $>30.0 \times 10^9/L$.

4.4 Definition of Dose Limiting Toxicities and Criteria in Phase I:

Dose limiting toxicities will be according to the NCI CTEP criteria Common Terminology Criteria for Adverse Events version 4.0[44]. A non-hematologic dose-limiting toxicity (DLT) is defined as a clinically significant (as assessed by treating physician) grade 3 or 4 adverse event or abnormal laboratory value (according to CTCAE criteria) assessed by treating physician as related to study drug (and unrelated to disease progression, intercurrent illness, or concomitant medications) occurring during the first 28 days on study. A hematologic DLT is defined as severe myelosuppression with a hypoplastic marrow with less than 5% cellularity and no evidence of leukemia 42 days from start of therapy. This will define severe and delayed myelosuppression not related to persistent leukemia and likely related to treatment.

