d. If DLT's are observed in 2/6 or more patients, this dose level would exceed the MTD, and the induction chemotherapy dose will be reduced to vosaroxin at a dose of 50 mg/m² IV on days 1 and 4 in the first cycle (induction 1) for a total dose of 100 mg/m²/cycle and the decitabine will be reduced to 20 mg/m² IV for only 4 consecutive days (Days 1 to 4). Six patients will be treated to evaluate the safety of this schedule, and after consultation with and approval of the PI. If DLTs are observed in 0-1/6 in phase I, the study will open broadly for the phase II at this schedule at this dose schedule.

After the first 6 subjects have been treated with vosaroxin and decitabine at the selected MTD (either dose-level a, b, or d), and assessed for toxicity, a summary and rationale to continue enrollment will be provided by the study team to the IND Office including a separate cohort summary for each dose level tested. These will be reviewed by the IND Office Medical Monitor. The IND Office Medical Monitor will indicate whether the study may continue enrollment.

4.5 Induction Therapy in Phase II:

Following the phase I portion to ensure safety, all subsequent patients will receive the following induction regimen (induction 1):

- a. Vosaroxin intravenously on days 1 and 4 at a dose of 70 mg/m² for a total dose of 140 mg/m²/cycle (days 1 and 4), or the final induction dose (MTD) determined in phase I.
- b. Decitabine IV at a dose of 20 mg/m² for 5 consecutive days (days 1 to 5), or the final induction dose (MTD) determined in phase I.

The 70mg/m² day 1 and 4 dosage of vosaroxin has been implemented in the REVEAL-I study (single agent vosaroxin in elderly AML) and was felt to be as efficacious as the 90 mg/m² dose with a lower incidence of mucositis. Based on our current experience and the data from REVEAL 1 we would like to request IND approval to reduce the vosaroxin induction dose from 90 mg/m² days 1 and 4 to 70 mg/m² days 1 and 4 with the intention of decreasing toxicity while maintaining equivalent efficacy.

Treatment may be repeated every 4-7 weeks. If a dose is missed, the patient may take the missed dose if it has been less than 48 hours.

Patients, who have not achieved any response (CR, CRp, Cri) following the initial induction (induction 1) course, can receive one additional induction course (induction 2) at the same dose as induction 1 or other dose modifications for re-induction may be made in the best interest

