If clinically significant grade 2 toxicity occurs during a course of induction or consolidation therapy, and it is unresponsive to optimal treatment and is thought to be possibly related to vosaroxin treatment, vosaroxin treatment may be withheld after the onset of an event until the adverse event (AE) has returned to baseline or \leq grade 1. If the AE has returned to baseline or \leq grade 1 within the 5-day induction or 5-day consolidation treatment interval from the start of therapy, treatment may resume at the same dose, but missed doses will not be made up. If the AE has returned to \leq grade 1 before administration of the next cycle, no dose reductions will be made with subsequent cycles.

If grade 3 or greater toxicity occurs during a course of induction or consolidation therapy, and it is unresponsive to optimal treatment and is thought to be possibly related to vosaroxin treatment, vosaroxin treatment may be withheld after the onset of an event until the AE has returned to baseline or \leq grade 1. If the AE has returned to baseline or \leq grade 1 within the 5-day induction or 5-day consolidation treatment interval from the start of therapy, treatment may resume but at a reduced dose. Reduce the dose of vosaroxin by one dose level as described in section 4.7.4 for the day 4 dosage of that cycle only. Missed doses will not be made up. In subsequent cycles of therapy, the dose of vosaroxin will remain at the reduced dose level for each subsequent cycle in combination with decitabine at a dose of 20 mg/m^2 intravenously for 5 consecutive days (Days 1 to 5). If the toxicity recurs or persists in spite of reducing the vosaroxin dose to, further dose reductions as outlined in section 4.7.4 will be allowed. If the toxicity recurs or persists after reducing to the lowest dose level, as described in section 4.7.4, then no further dose reductions will be permitted and the patient will be taken off study unless otherwise discussed with the PI.

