- A life-threatening adverse drug experience- any adverse experience that places the patient, in the view of the initial reporter, at immediate risk of death from the adverse experience as it occurred. It does not include an adverse experience that, had it occurred in a more severe form, might have caused death.
- Inpatient hospitalization or prolongation of existing hospitalization
- A persistent or significant incapacity or substantial disruption of the ability to conduct normal life functions.
- A congenital anomaly/birth defect.

Important medical events that may not result in death, be life-threatening, or require hospitalization may be considered a serious adverse drug experience when, based upon appropriate medical judgment, they may jeopardize the patient or subject and may require medical or surgical intervention to prevent one of the outcomes listed in this definition. Examples of such medical events include allergic bronchospasm requiring intensive treatment in an emergency room or at home, blood dyscrasias or convulsions that do not result in inpatient hospitalization, or the development of drug dependency or drug abuse (21 CFR 312.32).

- Important medical events as defined above may also be considered serious adverse events. Any important medical event can and should be reported as an SAE if deemed appropriate by the Principal Investigator or the IND Sponsor, IND Office.
- All events occurring during the conduct of a protocol and meeting the definition of a SAE must be reported to the IRB in accordance with the timeframes and procedures outlined in "University of Texas M. D. Anderson Cancer Center Institutional Review Board Policy for Investigators on Reporting Unanticipated Adverse Events for Drugs and Devices". Unless stated otherwise in the protocol, all SAEs, expected or unexpected, must be reported to the IND Office, regardless of attribution (within 5 working days of knowledge of the event).
- All life-threatening or fatal events, that are unexpected, and related to the study drug, must have a written report submitted within 24 hours (next working day) of knowledge of the event to the Safety Project Manager in the IND Office.

Unless otherwise noted, the electronic SAE application (eSAE) will be utilized for safety reporting to the IND Office and MDACC IRB.

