10.3 Statistical Design

Phase I

. In phase I portion of the study the MTD is defined as the highest daily oral dose evaluated at which $<33\%$ of patients experience a DLT. Six patients will be treated. If clinically significant drug related Grade 3-4 toxicity is observed during the first cycle in 0-1 patient out of 6 patients, this will define a safe schedule and the study will open broadly for the Phase II portion. If drug related Grade 3-4 toxicity is observed in 2 or more of 6 patients, this dose will exceed DLT, and a lower dose schedule will be investigated in an additional 6 patients. Please refer to Section 4.4. The dosing algorithm is presented in Table?.

Table 7. Dosing algorithm

Dose Level	Vosaroxin D1&D4	Decitabine
-3	50mg/mL	20 mg/m ² (Days 1-4)
-2	50 mg/m ²	20 mg/m ² (Days 1-5)
-1	70 mg/m ²	20 mg/m ² (Days 1-5)
0	90mg/m ²	20 mg/m ² (Days 1-5)

Phase II

Efficacy

The historical data suggested an ORR of 40% and with the assumption that the improved ORR is 60% the study will be stopped early if the observed patients' data suggest that:

$$\Pr(n > 0.6J \text{ data}) < 0.025$$

Here n is the overall response rate (ORR). That is, if at any time during the study we determine that there is a less than 2.5% chance that the average ORR is greater than 60%, we will terminate the study. The ORR is assumed to follow a non-informative prior of Beta (1.2, 0.8). The stopping boundaries for ORR, based on these assumptions and monitoring conditions are found in table 8. We will apply these stopping boundaries starting from the fifth patient and in cohorts of 5. For example, accrual will cease if only 2 or less than 2 patients experience overall response among the first 10 patients treated. The operating characteristics are summarized in table 8.

Table 8. Stopping boundaries for ORR

Number of patients evaluated	5	10	15	20	25	30	35	40	45	50	55	60
------------------------------	---	----	----	----	----	----	----	----	----	----	----	----

for response												
Number of patients with response (i.e., CR, CRp or CRi)	0	0-2	3-5	6-7	8-9	10-12	13-15	13-17	18-20	21-22	23-25	26-28

Table 9. Operating characteristics for monitoring of overall response rate

True overall Response Rate	Early Stopping Probability		Sample size		
			25%, 50%, 75%		
0.35	0.974		10	15	30
0.40	0.888		15	20	35
0.45	0.702		15	35	60
0.50	0.442		30	60	60
0.55	0.209		60	60	60
0.60	0.079		60	60	60
0.65	0.027		60	60	60

Toxicity Monitoring

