Following are the rules for the monitoring of toxicities in the Phase II portion of the study. Toxicity will be defined as clinically significant non-hematologic drug related grade 3 or higher adverse events. The probability of toxicity is denoted by PE. We assume PE – beta (0.6, 1.4). Our stopping rule is given by the following probability statement: Probability (PE > 0.30 | data) > 0.975. That is, we will stop the study if, at any time during the study, we determine that there is more than 97.5% chance that the toxicity is more than 30%. This stopping rule will be applied in each cohort. The stopping boundaries for clinically significant toxicities observed during the first cycle, based on these assumptions and monitoring conditions found in table 10. We will apply these stopping boundaries starting from the fifth patient and in cohorts of 5. For example, accrual will cease if 4 patients experience clinically significant toxicities during the first cycle among the first 5 patients treated. The operating characteristics are summarized in table 11.

Table 10. Stopping boundaries for Phase II toxicities

The number of patients evaluated for toxicities	5	10	15	20	25	30	35	40	45	50	55	60
The number of patients with DLTs	4	5-6	7-8	9-10	11-12	13-14	15-16	17-18	19	20-21	22-23	24-25

Table 11. Operating characteristics

True Toxicity Rate	Early Stopping Probability	Sample Size		
		25 th percentile	Median	75 th percentile
0.10	0.008	60	60	60
0.20	0.010	60	60	60
0.30	0.082	60	60	60
0.40	0.474	30	60	60
0.50	0.906	15	25	40

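### The Phase I DLT definition stops at grade 4, so a patient whose only qualifying event is a drug-related death is not counted in the 2-of-6 dose rule

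*Combined protocol and SAP*

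**What the plan says.** Section 4.4 grades DLTs by CTCAE v4.0. It defines the non-hematologic DLT as a "clinically significant (as assessed by treating physician) grade 3 or 4 adverse event or abnormal laboratory value" that the treating physician judges related to study drug, in the first 28 days. The only other route to a DLT is hematologic: a marrow under 5% cellularity without leukemia, 42 days from the start of therapy. With 0 or 1 DLT in six evaluable patients the level is the MTD; with 2 or more, six further patients are treated at a lower level.

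The same grade limit appears in two other statements of the rule:

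- Section 3.2: "If clinically significant, study drug related grade 3-4 toxicity is observed during the first cycle in 1 or less of 6" evaluable patients, the study moves to Phase II.
- Section 10.3, Phase I: "If clinically significant drug related Grade 3-4 toxicity is observed during the first cycle in 0-1 patient out of 6 patients", the schedule is called safe.

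Other parts of the protocol leave the upper grade open:

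- Section 10.3, Phase II monitoring: "Toxicity will be defined as clinically significant non-hematologic drug related grade 3 or higher adverse events".
- Section 4.7.3, dose modification: "If grade 3 or greater toxicity occurs during a course of induction or consolidation therapy".

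**The concern.** On the scale that Section 4.4 adopts, death related to an adverse event is grade 5. A definition that names only grades 3 and 4 therefore leaves out the most severe outcome. The hematologic DLT does not fill the gap, because a patient who died earlier has no marrow at day 42. The same fatal event would count toward the Phase II stopping rule but not toward the rule that selects the Phase II dose, and no reason is given for the difference.

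The gap is narrow. A fatal toxicity that was first recorded as a clinically significant, drug-related grade 3 or 4 event within 28 days already counts. Only patients whose sole qualifying event is the death are missed.

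The decision turns on 2 of 6, so one uncounted patient can reverse it. The protocol describes this as the first clinical trial of the combination and gives ensuring safety as the purpose of Phase I.

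**Working it through.** **Text comparison.** The protocol gives no operating characteristics for the 2-of-6 rule, so there is no stated figure to reproduce. Take a cohort of six with one grade 4 DLT and one drug-related death with no earlier countable event:

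- As written: count = 1, and the level is declared the MTD.
- With grade 5 included: count = 1 + 1 = 2, and the dose is reduced.

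**Inputs.** From Section 4.4: six patients per level, and a level passes with 0 or 1 DLT. Assumed, because the protocol does not give them:

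- *a*, the proportion with a countable grade 3-4 DLT: 10%, 15%, 20%.
- *d*, the proportion whose only qualifying event is drug-related death: 2% to 10%, with lower values below.
- A patient who dies early stays among the six evaluable patients. The protocol does not define evaluable.

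The 7% column matches the 30-day mortality quoted in Section 2.3.3 for single-agent decitabine. It is a reference point only: drug-related death-only events are a subset of all deaths, and this regimen is a combination.

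**Formula.** P(pass) = (1−p)^6 + 6p(1−p)^5, with p = *a* as written and p = *a* + *d* if grade 5 counts.

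For *a* = 0.15 as written: 0.85^6 + 6 × 0.15 × 0.85^5 = 0.377 + 0.399 = 0.776. With *d* = 0.05 counted, p = 0.20: 0.262 + 0.393 = 0.655.

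| *a* | As written | *d* = 2% | *d* = 5% | *d* = 7% | *d* = 10% |
|---|---|---|---|---|---|
| 10% | 0.886 | 0.844 | 0.776 | 0.729 | 0.655 |
| 15% | 0.776 | 0.729 | 0.655 | 0.606 | 0.534 |
| 20% | 0.655 | 0.606 | 0.534 | 0.487 | 0.420 |

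The corrected count is never below the written count. The difference in pass probability is therefore the chance that the written rule passes a level the corrected rule would reduce. At *a* = 15% it is 0.05, 0.12, 0.17 and 0.24 for *d* = 2%, 5%, 7% and 10%. At smaller death-only rates it is 0.012 (*d* = 0.5%) and 0.024 (*d* = 1%).

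**Given exactly one death-only patient** (*a* = 15%, *d* = 5%), each of the other five has a countable DLT with probability 0.15/0.95 = 0.158:

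- As written, the level passes with at most 1 of these 5: 0.820.
- With the death counted, it passes only with 0 of 5: 0.842^5 = 0.423.

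**Two or more death-only patients in six** is uncommon: 0.006, 0.033, 0.061 and 0.114 for *d* = 2%, 5%, 7% and 10%.

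**The case against.** The strongest reply is that few patients are affected. The severe toxicities tabulated for vosaroxin with cytarabine (sepsis, pneumonia, mucositis) would normally be recorded at grade 3 or 4 before they proved fatal, and so would count. Leukemia deaths are excluded by definition. The death-only rate could be under 1%, where the effect is about 0.01 to 0.02. This stands, and it is why the larger figures are not expected effects.

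The wording may also be loose drafting. Section 4.6 uses grade 3-4 for dose reductions of the kind that Section 4.7.3 describes with open-ended wording, and Table 10 labels the Phase II events as DLTs. The 4.7.3 wording governs dosing of living patients, so it is weak evidence of intent on deaths. An investigator would probably count a drug-related death anyway. All of this is plausible, but the written rule does not say it, in any of its three statements.

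Oversight exists as well. Under Section 9.3, "all SAEs, expected or unexpected, must be reported to the IND Office, regardless of attribution". Section 4.4 adds "The IND Office Medical Monitor will indicate whether the study may continue enrollment", and Section 4.2 says "Once approved, the Phase II portion of the study will be opened". That review would probably catch the case, but it does not alter the DLT count or require a dose reduction. Section 10.2 includes the six MTD patients in the Phase II 60, so their deaths could enter Phase II monitoring; that boundary (4 of the first 5) is much looser than 2 of 6.

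Finally, Section 4.5 already names 70 mg/m² for Phase II, which limits the practical reach. It keeps the MTD found in Phase I as an alternative, so the rule still has force.

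**Conclusion.** The concern holds. All three statements of the Phase I rule stop at grade 4, and no other Phase I text brings in drug-related death. Followed literally, the rule can declare a dose the MTD when counting the death would have required a reduction. With assumed grade 3-4 DLT rates of 10% to 20%, the chance that the two readings lead to different decisions is about 0.04 to 0.24 for death-only rates of 2% to 10%. At a 15% DLT rate it is about 0.01 to 0.02 for death-only rates of 0.5% to 1%. These figures illustrate sensitivity; the protocol gives none of the rates, and they assume that early deaths remain evaluable. Existing oversight makes harm unlikely, but the written safety rule should give the right count without relying on discretion. The change should be made.

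**What to change.** In Sections 3.2, 4.4 and 10.3 (Phase I), replace the grade 3-4 limit with grade 3 or higher, as in the Phase II monitoring text, so that a drug-related death in the first 28 days is a DLT. It would help to state in the same sentence that a patient who dies of drug toxicity in that window is evaluable.

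The cost is wording in three sections. No data, patients, boundaries or calculations change. As an optional tidy-up, the Table 10 row now labelled DLTs could carry the name of the Phase II toxicity defined just above it.
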